8. COMPARATORS

This section details the main independent variables that will be used to compare outcomes of HRQoL, sequencing of treatment regimens and kidney function.

In all 3 study aims we will be comparing both the frequency of use of first, second and third line and beyond therapies (SSAs, bevacizumab, cytotoxic chemotherapy, everolimus, Interferon alpha, embolization, PRRT, small molecule TKIs) and the effects of their ordering/sequencing on other secondary outcomes (i.e.: symptom burden, survival and adverse toxicity). These interventions have been selected as they are listed as potential biological therapies, liver directed therapies or chemotherapies that are routinely available to NET patients, and for which there is no clear consensus as to the effectiveness of their ordering (or concomitant use).

8.1. Aim 1 (Frequency of treatment regimens)

In this aim we will describe the frequencies of treatment regimens by line of therapy and multi-line sequences. Information from Aim 1 will also be used – with input from the Patient Advocacy Committee (PAC) and Clinician Group – to finalize the comparators for Aims 2 and 3.

8.2. Aim 2 (Treatment selection and outcomes)

With input from the Patient Advocacy Committee (PAC) and Clinician Group we will examine predictors of treatment selection and outcomes of overall survival and disease progression using chosen comparators from aim 1. To do this we will need to carefully pull individual patient level data from the CDM and conduct targeted chart reviews of each patient's EMR.

8.3. Aim 3 (Comparative effectiveness of PRRT regimens)

Comparators will be PRRT with vs. without administration of other systemic therapies and PRRT before vs. after embolization therapy and chemotherapy. Comparisons will be with respect to renal toxicity, disease progression, patient-reported symptoms, and HRQoL. Heterogeneity of treatment effects will be assessed for these comparators in subgroups defined by tumor grade and type (GEP or lung NETs).

9. STATISTICAL ANALYSIS PLAN

9.1. General Statistical Approach

Continuous variables will be summarized using descriptive statistics such as mean, standard deviation, median, minimum and maximum. Categorical variables will be summarized by count and percentage. Group comparisons will be assessed using chi-squared or Fisher's exact tests for categorical variables, and an analysis of variance or Kruskal-Wallis tests for continuous variables where appropriate. Adjustment for covariates listed in Tables 2 and 3 will be explored for each analysis as needed to account for potential confounding effects. Time-dependent covariates will be incorporated to capture changes in covariates across time, as necessary. Inclusion of random effects to account for potential clustering of patients treated at the same study site will be explored. Depending on the rate and pattern of missing data, multiple imputation methods may be considered to account for data missing at random or attributable to non-ignorable drop-out [56]. Planned study outcomes are summarized in Table 4.

9.1.1. Aim 1

Mixed effects regression models will be utilized to assess changes in HRQoL and symptoms within and between groups (i.e.: different treatment regimens) over time. Random effects will be employed to account for the longitudinally correlated nature of repeated questionnaire measurements. Should completion of questionnaires deviate from the planned assessment time points, a spatial power covariance structure will be included to account for the unequal time spacing between assessments within a patient.

9.1.2. Aim 2

Multinomial logistic regression models will be used to identify which patient, clinical, and tumor characteristics (Table 2), and patient attitudes and beliefs (Table 3) influence selection of treatment regimens for each line of treatment. The conditional Cox regression model proposed by Prentice, Williams, and Peterson (PWP) will be used to simultaneously model the gap times between initial diagnosis and first progression and between subsequent progressions as a function of the prognostic factors of interest for progression-free survival. The baseline hazard is expected to differ for first-line therapy and for subsequent lines of therapy, thus event-specific estimates will be obtained. A robust sandwich estimator will be used to account for potential dependencies within patients. Overall survival will be evaluated using a Cox regression model.

9.1.3. Aim 3

Statistical analyses for Aim 3 will mimic those outlined in Aims 1 and 2, but with a special interest in evaluating the effectiveness of PRRT regimens on each of the outcomes. PRRT regimens to be evaluated include: PRRT alone, PRRT ± other biological therapy, PRRT ± prior embolization. Additionally, the PRRT isotope used (^{177}Lu vs ^{90}Y) will be evaluated.

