2.1. Purpose

The purpose of this project is to partner with patients on CER to achieve the goal of mitigating toxicity and optimizing effectiveness and sequencing of therapy for patients with NETs.

In order to achieve this overall goal, we have four specific aims. Aim 1 addresses the patient question of ‘what therapy would be best to try next?’ in the context of symptom burden and quality of life. Aim 2 addresses patient concerns surrounding the question of ‘If I were to take this option now, what treatment options will be closed off to me in the future’, by examining patient and tumor factors associated with overall survival and disease progression. Aim 3 leverages the data obtained in aims 1 and 2 to inform a comparative effectiveness study of contemporary concern, with a focus on patient-centered quality of life and toxicity outcomes. Aim 4 will aid dissemination of our study results and contribute to PCORnet rare disease infrastructure.

AIM1: To describe the frequency of treatment regimens received by line of therapy, and examine their association with symptom burden and changes in 6, 12 and 18 month HRQoL outcomes. The influence of patient preferences, beliefs, attitudes, and experience of care on choice of these treatment regimens will also be examined.

Expected outcomes of aim 1: This aim will enable the ascertainment of patient-reported outcomes (PROs) related to the experience of symptom burden and toxicities for various therapies (and combination treatments) and explore the patient’s attitudes and beliefs that impact the choice of treatment sequencing beyond the basis of clinical and tumor characteristics. Descriptive analyses of these important PROs (that do not exist in the patient’s EMR will determine what combinations of therapy are being used, and the changes in symptoms and HRQoL associated with these therapeutic choices.

AIM 2: To examine the association of patient, clinical, and tumor characteristics on the selection of first-line and beyond treatment regimens and compare the effects of common treatment sequences on frequency of subsequent treatments received and outcomes of overall survival and disease progression.

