6.3. Patient surveys

Table 3 outlines the measures that will be collected from the baseline and follow-up surveys which will be administered through the PHR. The UICC has prepared a data dictionary for the baseline survey. Data dictionaries will also be made available for the follow-up surveys.

Whilst many of the current survey items are derived from validated instruments, or have been used in empirical research studies, we are receiving input from the clinician group and patient advocacy organization committees to adapt and tailor many of these items to a NET population. We anticipate that several physical and psychosocial themes may be missing from the HRQoL questionnaires that we are using which may be important to patients and/or help clinicians in their patient interactions. Therefore, in working with our patient partners and clinician groups we may identify further themes, concepts and items impacting on HRQoL and incorporate these additional measures into the baseline and study follow-up questionnaires.

Table 3: Overview of concepts and measures examined on the baseline and follow-up surveys

Concept/measure	Baseline Survey	Follow-up Surveys
Sociodemographic data (date of birth, sex and gender orientation, race, marital status, ethnicity, state of residence, household income, highest level of educational attainment, health literacy)	X	
Height and weight	X	X
Health Related Quality of Life, QLQ-C30, QLQ-GINET21, Other impacts of cancer (worry, other life events)	X	X
Norfolk Carcinoid Symptom Score [47]	X	X
History of chronic conditions (20-item checklist)[48]	X	
Preferences and attitudes (quality vs quantity of life [49], preferred decision-making role [50, 51], family's role in decision-making)	X	
Attitudes (fatalistic thinking, spirituality) [52], Experiences of care (physician communication, coordination and responsiveness of care [53], actual decision-making role [50]	X	X
Self-reported treatments, including over-the-counter medications and supplements	X	X

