7.2. Secondary Outcomes

- 1) **Norfolk Carcinoid Symptom Score.** The Carcinoid Symptom Score [49] contains 13 questions, where question 1 has 3 queries about flushing, with a maximum of 3 points; question 3 has 4 items inquiring about respiratory symptoms, with a maximum score of 4. There are 3 questions about gastrointestinal symptoms for a total of 3 points, 3 questions related to physical functioning for a total of 3 points, and 3 questions related to cardiovascular disease for a total of 3 points; the remaining 2 questions are about family and personal medical history. The answers to the questions are quantified as “0” (no symptom) and “1” (symptom present), so the higher the score the worse is the symptom burden, from a score of “0” to “18.”
[Time Frame: Change in score across baseline, 6, 12, and 18 month time points.]
- 2) **Experiences with cancer care (from CANCORS).** 13 items assess patients' experiences with interpersonal aspects of cancer care [53], including physician communication (five items), nursing care (two items), and coordination and responsiveness of care (six items). The scores in each domain are converted to 100-point scales, with 0 representing the worst possible care and 100 representing optimal care. Patients can also rate the overall quality of their health care since cancer was diagnosed on a 5-point scale ranging from excellent to poor.
[Time Frame: Change in score across baseline, 6, 12, and 18 month time points.]

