9.3. Addressing confounding

With a large, proposed sample size of approximately 3,000 patients, we will minimize the effects of confounding on treatment effect estimates by adjusting for factors associated with treatment selection within the context of multivariable models. Known and hypothesized factors associated with treatment selection include but are not limited to the following: sociodemographic (age, sex, race, ethnicity, marital status, income), health status (BMI, smoking history, comorbidities), disease (site, stage, grade, nodal status), prior therapy use (PRRT, everolimus, sunitinib, liver-directed therapies, chemotherapy, surgery), and patient-reported preferences, attitudes, beliefs and experience of care. Determination of confounding factors that may warrant adjustment will be guided by the results from the multinomial logistic regression models evaluating factors associated with selection of treatment regimens (Aim 2). Furthermore, the use of time-dependent variables for treatment and potential confounders (where appropriate) will minimize the effects of survivor treatment selection bias.

As a novel project aimed to evaluate the complex interplay between patient, disease, and treatment factors on toxicity, HRQoL, and survival outcomes, the statistical analysis plan will be refined once descriptive information from Aims 1 and 2 is available for consented patients. For example in Aim 3, PRRT sits amongst a growing number of therapeutic options in metastatic well-differentiated NETs, including pharmacological (i.e.: mTOR inhibitor everolimus and the tyrosine kinase inhibitor sunitinib), hormonal and liver-directed therapies (i.e.: embolization (bland, chemo, radio)), and surgical approaches. Therefore, we need to be mindful of this multimodal treatment algorithm wherein patients may undergo a variety of treatment options at tumor progression(s).

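### Section 9.1.2 models survey-measured attitudes as influences on every line of treatment, although for lines begun before Survey #1 they are measured after the choice was made

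*Protocol*

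**What the plan says.** **The model.** Protocol 9.1.2 (Aim 2) will identify which clinical and tumor characteristics and which "patient attitudes and beliefs (Table 3) influence selection of treatment regimens for each line of treatment". The sentence has no condition on when the items were measured. Section 2.1 confirms that first line is in scope, since Aim 2 is "on the selection of first-line and beyond treatment regimens". Aim 1 in the same section says: "The influence of patient preferences, beliefs, attitudes, and experience of care on choice of these treatment regimens will also be examined".

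**The measurement.** Table 3 (section 6.3) takes these items from the patient surveys only. Preference items (quality versus quantity of life, preferred decision role, family role) are asked at baseline only. Fatalistic thinking, spirituality, experience of care and actual decision-making role are asked at baseline and follow-up. Section 7.2 describes the overall care rating as follows: "Patients can also rate the overall quality of their health care since cancer was diagnosed".

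**The timing.** Survey #1 is the last enrolment step, after consent (5.7). Eligible diagnoses run from 1/1/2019 to 12/31/2023 (4.2). Therapies are dated from diagnosis (7.1, treatment sequencing). Table 8 (section 11) gives first enrolment as due 9/30/2021 and projected for 4/29/2022. Appendix B, under other recruitment methods, allows prevalent cases to be recruited at routine follow-up.

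**Adjustment.** Section 9.3 lists "patient-reported preferences, attitudes, beliefs and experience of care" among factors associated with treatment selection, and adds: "Determination of confounding factors that may warrant adjustment will be guided by the results from the multinomial logistic regression models".

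**The concern.** A model of what influences a choice needs predictors that stood before the choice. A patient diagnosed in 2019 or 2020 may have started, and perhaps finished, first-line therapy before any study survey existed. The attitudes that patient then reports may have been shaped by the treatment, its toxicity or its result. Fitted to such patients, the 9.1.2 model reads the relation in one direction when it may run in the other.

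How preferences shape treatment choice is one of the study's stated questions, so a reversed finding would touch a planned result. There is a secondary route through 9.3: an item that differs by regimen because of the regimen would show up in the selection models, and those models guide which variables are considered for adjusting treatment effects.

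**Working it through.** The protocol gives no sample size, power or effect figure for the treatment-selection models, so there is none to reproduce. The check is calendar arithmetic followed by the condition for bias.

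**Inputs.** Diagnosis window 1/1/2019 to 12/31/2023 (4.2). Earliest survey 4/29/2022, projected (Table 8, milestone B12), or 9/30/2021 as originally due. One month is taken as 30.44 days.

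**Step 1: share of the window before any survey.**
- Window length: 365 + 366 + 365 + 365 + 365 = 1,826 days.
- 1/1/2019 to 4/29/2022: 1,214 days; 1,214/1,826 = 66.5%.
- With the due date of 9/30/2021: 1,003 days; 1,003/1,826 = 54.9%. The point does not rest on the projected date.

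**Step 2: shortest possible interval from diagnosis to survey, for diagnoses on those 1,214 days.**
- Maximum 1,214 days (1,214/30.44 = 39.9 months); median about 607 days (19.9 months).
- Share of those days with an interval above m months, (1,214 − 30.44m)/1,214: 85.0% for 6 months, 69.9% for 12, 39.8% for 24.

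**Step 3: when the survey must follow first-line start.** The protocol gives no time from diagnosis to first line, so a gap of g months is an assumption. The share of the window's days on which a diagnosis leads to first line before any survey is possible is (1,214 − 30.44g)/1,826:

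| Assumed g (months) | Share of window days |
|---|---|
| 0 | 66.5% |
| 3 | 61.5% |
| 6 | 56.5% |
| 12 | 46.5% |
| 24 | 26.5% |
| 36 | 6.5% |

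The long gaps belong in the range. The therapies listed in sections 7.1 and 8 omit surgery, so a listed first line may start late or never. No figure is claimed for diagnoses after 4/29/2022. Appendix B says registry cases are typically abstracted 4 to 6 months after diagnosis, while the clinic route may be quicker.

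**Step 4: what makes the estimate wrong.** Suppose an item had no relation to regimen before treatment and regimen r then shifts its mean by δ_r. Assuming a normal item with common variance σ², the log-odds slope for regimen r against s is (δ_r − δ_s)/σ². A shift shared by all regimens gives zero; a regimen-specific shift gives a non-zero slope with no influence on choice behind it. The protocol has no data on the δ values, so the bias cannot be sized.

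**Step 5: which items are exposed.**
- *Most exposed:* experience of care, whose overall rating spans the time since diagnosis and so includes any first line already begun, and actual decision-making role, which describes decisions already taken. Neither is in the 9.1.2 sentence. Experience of care enters through Aim 1 and 9.3; actual decision-making role appears in Table 3.
- *Exposed:* the preference and attitude items asked at baseline only.
- *Less exposed:* fatalistic thinking and spirituality, which are likely to be more stable.

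**Step 6: do the stated safeguards reach this?** Sections 9.1 and 9.3 allow time-dependent covariates. They can update repeated items for later lines, but they cannot create a value from before Survey #1, and baseline-only items are never updated.

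**The case against.** The strongest reply is that this is detail for later. Section 9.2.2 calls the Aim 2 analyses exploratory, 9.3 says the analysis plan will be refined after descriptive results, and 2.1 frames the clinical part of Aim 2 as association. That limits the weight but does not remove the point. The 9.1.2 sentence is unconditional, covers every line and speaks of influence, as does Aim 1, and no passage restricts it to lines begun after the survey.

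Three stronger readings are tempting and should not be drawn.

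- *That about two thirds of patients are affected.* The 66.5% counts days. Section 5.3 aims the searches at incident and recently diagnosed patients, and the high-PPV phenotype in Appendix B is applied to patients not known to have died, so enrolment need not be even over diagnosis dates.
- *That any item changed by treatment biases the selection model.* Step 4 shows that the change must differ between regimens.
- *That 9.3 would wrongly adjust for post-treatment variables and should exclude them.* Section 9.3 lists candidates and leaves the choice open. A late-measured preference may also be the only available proxy for confounding by preference. Which bias is larger is unknown, so a ban is not supported.

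**Conclusion.** The point holds in a limited form. For lines begun before Survey #1, section 9.1.2 uses predictors measured after the outcome, and calling the result an influence on selection is not supported. Lines begun after the survey that supplies the item are not affected.

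The size is known only as calendar time: 66.5% of the diagnosis window precedes any possible survey (54.9% at the original due date). Under assumed gaps of 0 to 36 months from diagnosis to first line, the survey must follow first-line start for diagnoses on 66.5% down to 6.5% of the window's days. The share of patients and the bias in any coefficient cannot be derived. A false finding needs regimens that shift an item differently, which is plausible for experience of care and decision role and less so for fatalism and spirituality. For 9.3 this is a risk the wording permits, not an error it commits. The change is worth making because it concerns a stated study question and costs little.

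**What to change.** 1. In 9.1.2, and in the matching Aim 1 analysis, use survey-measured attitude, belief, preference, decision-role and experience-of-care items as predictors of selection only for lines begun after the survey that measured them.
2. For lines begun earlier, report the relation as an association, not as influence.
3. Report how many patients completed Survey #1 before and after first-line start.
4. In 9.3, do not require exclusion. Where such an item was measured after the treatment in question began, show the treatment effect with and without it.

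The Table 2 clinical and tumor variables are outside this restriction. The work is a wording change and a comparison of two dates already held: therapy start (7.1) and baseline survey completion, from which the follow-up surveys are scheduled (5.10.3). The cost is that fewer patients inform the first-line attitude models, and those who do will tend to be the more recently diagnosed or those whose listed therapy started late.

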- 3) **Progression-free survival (PFS).** Time to event data will be calculated from the index date (date of diagnosis) to the earliest of disease progression, death from any cause or end of study follow-up (12/31/2023). Acknowledging that patients may have more than one progression over the study period endpoints of median time to first progression (time from initiation of first-line therapy to progression) and time to second progression (time from second-line therapy initiation to progression) will be observed from targeted chart reviews at annual intervals. In collaboration with our clinician group we have discussed the various limitations of the application of the RECIST 1.1 criteria in NETs. These limitations include an overemphasis on tumor progression (given the low proliferation rate of GEP-NETs, monitoring changes in tumor size is suboptimal), and RECIST 1.1 criteria do not reflect overall tumor load or response to therapy in metastatic patients (i.e.: issues with clinical significance of radiologic progressions). Optimizing the management of NET patients therefore requires considering clinical, biological, and pathological aspects of the tumor. We have therefore chosen to categorize disease progression as DISEASE CONTROL (complete or partial response & stable disease), PROGRESSION (with no treatment change), PROGRESSION (with treatment change), and INDETERMINATE. This clinician-anchored approach has been found to be an optimal and valid method (versus RECIST1.1) for evaluating real-world tumor burden endpoints from EMR data [55].
[Time Frame: median time to progression, assessed annually via chart review]
- 4) **Overall Survival (OS).** Time to event data will be calculated from the date of diagnosis (index date) to the date of death from any cause, or end of study follow-up (12/31/2023). Death and vital status (death date, cause of death) will be pulled from the death table, and death cause table in the CDM. This data may be supplemented from site linkage to the social security death index or cancer registry sources (where possible). Given the prospective nature of the study we also have potential for passive surveillance/follow-up with participant/next of kin with information collected on our follow-up questionnaires.
[Time Frame: Up to 5 years]

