- 5) **Adverse toxicities.** We will assess incident acute renal failure, dialysis and liver failure during study follow-up (from diagnosis codes in the CDM). The occurrence of these events will be compared in reference to the treatment regimens received.
[Time Frame: Up to 5 years]

Table 4: Overview of Primary and Secondary outcomes for NET-PRO by project aims

Primary or Secondary	Name of Outcome	Specific Measure(s)/ Instrument(s) to Be Used	Timepoints (mths)	PROMIS and/or Core Outcome Set ?	Powered Yes/No/NA
Aim 1					
Primary	Health related Quality of Life (HRQoL)	EORTC QLQ-C30 EORTC QLQ-GI.NET21	0, 6, 12, 18	Yes	Yes
Secondary	Symptom inventory	Norfolk Carcinoid Symptom Score [49] Norfolk Carcinoid Symptom Score [49]	0, 6, 12, 18	No	No
Secondary	Experiences of care	Physician communication, coordination and responsiveness of care [62]	0, 6, 12, 18	No	No
Aim 2					
Primary	Sequencing of treatment regimens	-	0-60	No	Yes
Secondary	Progression-free survival	Time to event (Categorization of stable disease, disease progression with no change in treatment, disease progression with changes in treatment, and indeterminate)	0-60	No	Yes
Secondary	Overall survival	Time to event	0-60	No	NA
Secondary	Adverse toxicities	Incident acute renal failure, dialysis and liver failure during follow-up	0-60	No	NA
Aim 3					
Primary	Renal function	Creatinine clearance loss (per/Yr)	0, 6, 12, 18	No	Yes
Secondary	Adverse toxicities	CDM diagnosis codes for acute renal failure, dialysis and liver failure during follow-up	Up to 60	No	No
Secondary	Health related Quality of Life (HRQoL)	Changes in HRQoL and symptom scores	0, 6, 12, 18	No	No
Secondary	Renal toxicity (creatinine clearance) by PRRT isotope	Creatinine clearance loss (per/Yr) 177Lu vs 90Y	Up to 60	No	No
Secondary	Renal toxicity of PRRT by primary tumor location & grade 3 disease	Creatinine clearance loss (per/Yr) GEP-NETs vs lung NETs and G3	Up to 60	No	No

NA: Not applicable

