The primary objective of Aim 2 is to evaluate the effect of common treatment sequences on progression-free survival. A lack of historical data on the frequency and number of different variations of treatment sequences, and progression-free survival (PFS) differences by treatment and line of treatment coupled with the likelihood treatment sequences will further differ between the 14 sites taking part in this study make *any realistic and meaningful* sample size and power calculations impossible. Analyses for this aim will be exploratory, and will leverage the use of time-varying covariates in combination with the conditional Cox regression model proposed by Prentice, Williams, and Peterson (PWP) as a means of addressing the heterogeneity evidenced in the data. However, to put into perspective potential PFS differences that may be detected between two treatments using purely hypothetical situations, the below table summarizes power achieved for varying combinations of median PFS differences and number of patients per treatment arm. Calculations are based on the following assumptions: 1:1 treatment allocation, 48 months of uniform accrual and 12 months of follow-up, no loss to follow-up or switching treatments, unadjusted for confounders, and using the Lakatos approximation for a two-sided log-rank test with a 5% significance level.

Table 6: Power determination for changes in median PFS

Median PFS		N Per Treatment Arm	Power
Treatment 1	Treatment 2		
12 months	24 months	45	0.79
		50	0.83
24 months	36 months	175	0.80
		190	0.83

9.2.3. Aim 3

The primary objective of Aim 3 is to evaluate renal toxicity associated with the administration of PRRT as measured by creatinine clearance loss over time. We are expecting 2 mL/min/1.73m² annual decline in creatinine clearance based on averaged long-term follow-up with the most common PRRT isotope 177-Lu [34]. The repeated measures design with 180 subjects and 1 within-subject factor (time: baseline, 6 months, 12 months, and 18 months) achieves 100% power to detect creatinine clearance loss of 2 mL/min/1.73m² by 6 months, 4 mL/min/1.73m² by 12 months and 6 mL/min/1.73m² by 18 months, when the Wilks' Lambda approximate F test is used with a significance level of 0.05, and assuming an

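### PFS is defined with death as an event, but the PWP model assigned to it closes gaps only at progression, so as written it estimates a progression hazard ratio, not a PFS hazard ratio

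*Protocol*

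**What the plan says.** Section 7.2, item 3, runs PFS from diagnosis "to the earliest of disease progression, death from any cause or end of study follow-up (12/31/2023". Death is therefore an event. The same item adds separate endpoints that end at progression alone, such as "median time to first progression (time from initiation of first-line therapy to progression".

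Section 9.1.2 gives PFS one regression model, PWP. Its intervals are to "simultaneously model the gap times between initial diagnosis and first progression and between subsequent progressions", fitted "as a function of the prognostic factors of interest for progression-free survival". Event-specific estimates are planned. Nothing is said about a terminal event or a competing risk. Deaths are modelled only in a separate sentence: "Overall survival will be evaluated using a Cox regression model".

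Table 4 describes the PFS measure by disease status only ("Categorization of stable disease, disease progression with no change in treatment, disease progression with changes in treatment, and indeterminate") and does not mention death.

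On the weight of the analysis, section 9.2.2 states: "The primary objective of Aim 2 is to evaluate the effect of common treatment sequences on progression-free survival". The same section calls the Aim 2 analyses exploratory, and Table 4 lists PFS as a secondary outcome. Section 9.1.3 adds: "Statistical analyses for Aim 3 will mimic those outlined in Aims 1 and 2".

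**The concern.** Two stated rules disagree. The endpoint counts death; the intervals of the model named for that endpoint do not. An analyst who codes the gaps as section 9.1.2 describes them would record no event for a patient who dies before a recorded progression, so follow-up would in effect be censored at death. The resulting ratio compares progression hazards among patients still alive and progression-free. That is a legitimate quantity, but it is not PFS.

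The two ratios part company when regimens differ in death without recorded progression. The protocol gives some reason to expect such deaths. Grade 3 disease is included and described as having a poorer prognosis (section 1.1.4). Section 1.1.3 cites serious toxicity rates from 3.0% to 83.9% across treatment combinations, although it does not report deaths. Disease status is abstracted in one chart review near the end of follow-up (section 6.2) and assessed at annual intervals (section 7.2), so some patients may die before a progression is recorded. A regimen with more of these deaths could then look no worse in the analysis that carries the PFS label.

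**Working it through.** **1. The plan's own figure.** Table 6 gives power for median PFS differences. Inputs from section 9.2.2: 1:1 allocation, 48 months' uniform accrual (A), 12 months' follow-up (F), no loss to follow-up, two-sided 5% log-rank test. With exponential PFS, the event probability per arm is 1 − (e^(−λF) − e^(−λ(A+F)))/(λA), where λ = ln 2/median.

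- Median 12 months: 1 − (0.500 − 0.031)/2.773 = 0.831.
- Median 24 months: 1 − (0.707 − 0.177)/1.386 = 0.617.
- At 45 per arm, expected events are 45 × (0.831 + 0.617) = 65.2.

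A Lakatos-type log-rank calculation gives 0.795, 0.835, 0.801 and 0.832 for the four rows, against 0.79, 0.83, 0.80 and 0.83 in Table 6. The table reproduces and is not in dispute. It treats PFS as a single time-to-event endpoint.

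**2. Hazard ratio with and without deaths.** The documents give no rate of death without progression, so this step is an illustration. Assumptions:

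- Both regimens have the same progression hazard, λp = ln 2/24 = 0.0289 per month.
- Deaths without progression make up a share q of regimen A's PFS events, so A's hazard of such deaths is d = λp·q/(1 − q).
- Regimen B has hazard 2d.

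The progression-only ratio, B v A, is λp/λp = 1.00. The PFS ratio is (λp + 2d)/(λp + d) = 1 + d/(λp + d) = 1 + q. Median PFS is 24(1 − q) months for A and 24(1 − q)/(1 + q) for B.

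| q (assumed) | Progression-only HR | PFS HR | Median PFS, A v B (months) |
|---|---|---|---|
| 5% | 1.00 | 1.05 | 22.8 v 21.7 |
| 10% | 1.00 | 1.10 | 21.6 v 19.6 |
| 20% | 1.00 | 1.20 | 19.2 v 16.0 |
| 30% | 1.00 | 1.30 | 16.8 v 12.9 |

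A simulated Cox fit of the first gap at q = 20% (10,000 per arm, censoring uniform over 12 to 60 months) gave 1.03 with deaths censored and 1.25 with deaths as events. Both lie somewhat above the closed-form 1.00 and 1.20, which I attribute to sampling error; the closed form is what I rely on.

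**3. Events lost.** If a share q of PFS events goes uncounted and the hazard ratio is otherwise unchanged (a further assumption), Schoenfeld power is Φ(√D·|ln HR|/2 − 1.96). For Table 6's first row, D = 65.2 and HR = 0.5 give Φ(8.07 × 0.693/2 − 1.96) = Φ(0.84) = 0.80. Multiplying D by 0.95, 0.90, 0.80 and 0.70 gives 0.78, 0.76, 0.71 and 0.65.

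**The case against.** **Censoring at death is inferred, not stated.** The sentence in section 9.1.2 could be read as describing only the order of the PWP strata, with events taken from the PFS definition. Section 9.3 says the analysis plan will be refined, and section 13.3.1 treats the statistical analysis plan as a document with its own sign-off. It is true that the protocol never says to censor at death. But section 9.1.2 does more than leave a gap: it says where each interval ends, and that differs from section 7.2. A later plan would have to depart from one of them.

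**Excess mortality would not be hidden from the study.** A reader might infer that it would. The documents do not support that, because overall survival is a named outcome with its own Cox model. The loss is confined to the analysis labelled PFS.

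**The progression hazard ratio is valid in its own right.** A reader might infer that censoring at death assumes the dead would have progressed at the survivors' rate. A Cox-type model of the cause-specific hazard needs no such assumption, and 1.00 is the correct progression ratio in the illustration. The fault is in calling it PFS.

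**Time to first and second progression are separate endpoints.** They start from a line of therapy and properly omit death. A reader might infer that their medians will come out too long. That holds only against median PFS, which is a different endpoint. Against a cumulative incidence with death competing, censoring at death would overstate progression and shorten the median. No estimator is named, so there is no error to correct here.

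**Aim 3 may be little affected.** Section 8.3 compares disease progression, and Table 4 lists no PFS outcome under Aim 3. The point carries over only if an Aim 3 analysis is presented as PFS.

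**The size is assumed.** The protocol describes NETs as slow-growing with long survival, and participants must be alive to consent, so the lower end of the range may be the more realistic.

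**Conclusion.** The point holds as a mismatch between endpoint and model. As written, the model assigned to PFS yields a cause-specific hazard ratio for progression, not a hazard ratio for progression or death. Only its first gap, from diagnosis, matches the interval in section 7.2, and even there the event differs.

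Under equal progression hazards and a doubled hazard of death without progression, the PFS ratio would be 1.05 to 1.30 where the progression-only ratio stays at 1.00. This rests on constant hazards and on such deaths being 5% to 30% of the reference regimen's PFS events, a share the protocol does not give. If regimens do not differ in these deaths and few occur, the two ratios nearly coincide.

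It deserves correction because section 9.2.2 makes PFS the primary objective of Aim 2. Its weight is moderate, since the analysis is called exploratory and deaths are analysed separately as overall survival.

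**What to change.** Amend section 9.1.2 in one of two ways:

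1. State that each PWP gap closes at progression or death from any cause, whichever comes first, and that death ends all further risk. The first-gap estimate is then the PFS hazard ratio under section 7.2.
2. Relabel the PWP analysis as time to progression, reporting cause-specific hazards with death as a competing terminal event, and analyse PFS as defined in section 7.2 with a Cox model that counts death as an event.

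Align the PFS row of Table 4 by naming death among the events, and say in section 9.1.3 which version any Aim 3 analysis follows.

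The cost is a sentence or two in each place. Death dates are already to be collected (Table 2 and section 7.2, item 4), and Table 6 needs no change if PFS keeps its present definition.
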